10.4.3 Safety Analysis

Safety will be assessed through the analysis of the reported incidence of treatment-emergent AEs. Treatment-emergent AEs are those with an onset on or after the initiation of therapy, and will be graded according to NCI CTCAE v 4.03. A copy of CTCAE scoring system may be downloaded from: https://evs.nci.nih.gov/ftp1/CTCAE/CTCAE_4.03/CTCAE_4.03_2010-06-14_QuickReference_8.5x11.pdf.

The AEs will be coded using Medical Dictionary for Regulatory Activities (MedDRA), and summarized using system organ class and preferred term for all patients in the Safety Population. In addition, summaries of serious adverse events (SAEs), AEs leading to treatment

CONFIDENTIAL

STUDY DRUG: NIVOLUMAB

SARAH CANNON DEVELOPMENT INNOVATIONS STUDY NUMBER:

FINAL PROTOCOL DATE: 07 FEB 2020

BMT 24

VERSION 7

discontinuation, AEs by maximum NCI CTCAE grade, and AEs related to study treatment will also be presented.

Other safety endpoints including laboratory results and vital signs will be summarized for all patients in the Safety Population.

Concomitant medications will be listed and summarized and coded using the World Health Organization-Drug Dictionary.

10.4.4 Exploratory Analysis

The scope and details of the exploratory analysis, including correlative biomarker analysis, will be detailed in the Statistical Analysis Plan (SAP).

10.5 Analysis Time Points

10.5.1 Final Analysis

The final analysis of the study will occur when all enrolled subjects have received at least 2 cycles of nivolumab and have completed 12 month post-ASCT disease assessment.

10.5.2 Planned Interim Analysis

There is no planned interim analysis for this study.

11. SAFETY REPORTING AND ANALYSES

Safety assessments will consist of monitoring and recording protocol-defined AEs and SAEs, measurement of protocol-specified hematology, clinical chemistry, and other protocol-specified tests in the eCRFs that are deemed critical to the safety evaluation of the study drug.

The PI is responsible for recognizing and reporting AEs to the Sarah Cannon Development Innovations Safety Department (see Section 11.2). It is the Sponsor's responsibility to report relevant SAEs to the applicable local, national, or international regulatory bodies. In addition, Investigators must report SAEs and follow-up information to their responsible IRB according to the policies of that IRB.

The PI is also responsible for ensuring that every staff member involved in the study is familiar with the content of this section.

11.1 Definitions

11.1.1 Adverse Events

Adverse event means any untoward medical occurrence associated with the use of a drug in humans, whether or not considered drug-related. An AE can be any unfavorable and unintended sign (e.g., an abnormal laboratory finding), symptom, or disease temporarily associated with the use of a drug, without any judgment about causality. An AE can arise with any use of the drug (e.g., off-label use, use in combination with another drug) and with any route of administration, formulation, dose or including overdose.

CONFIDENTIAL

STUDY DRUG: NIVOLUMAB

SARAH CANNON DEVELOPMENT INNOVATIONS STUDY NUMBER:

FINAL PROTOCOL DATE: 07 FEB 2020

BMT 24

VERSION 7

11.1.2 Serious Adverse Event

An AE or a suspected adverse reaction (SAR) is considered “serious” if it results in any of the following outcomes:

- **Death**
- **A life-threatening AE**
- **Inpatient hospitalization of at least 24-hours or prolongation of existing hospitalization**
- **A persistent or significant incapacity or substantial disruption of the ability to conduct normal life functions**
- **A congenital anomaly/birth defect**

Important medical events that may not result in death, be life-threatening, or require hospitalization may be considered serious when, based upon appropriate medical judgment, they may jeopardize the patient or subject and may require medical or surgical intervention to prevent one of the outcomes listed in this definition. Examples of such medical events include allergic bronchospasm requiring intensive treatment in an emergency room or at home, blood dyscrasias or convulsions that do not result in hospitalization, or development of drug dependency or drug abuse.

It is important to distinguish between “serious” and “severe” AE, as the terms are not synonymous. Severity is a measure of intensity; however, an AE of severe intensity need not necessarily be considered serious. Seriousness serves as the guide for defining regulatory reporting obligations. “Serious” is a regulatory definition and is based on patient/event outcome or action usually associated with events that pose a threat to a patient’s life or vital functions. For example, nausea which persists for several hours may be considered severe nausea, but may not be considered an SAE. On the other hand, a stroke which results in only a limited degree of disability may be considered only a mild stroke, but would be considered an SAE. Severity and seriousness should be independently assessed when recording AEs on the eCRF and SAEs on the SAE Report Form.

11.1.3 Adverse Reaction

An adverse reaction means any AE caused by a drug. Adverse reactions are a subset of all SARs where there is a reason to conclude that the drug caused the event.

11.1.4 Suspected Adverse Reaction

Suspected adverse reaction means any AE for which there is a reasonable possibility that the drug caused the AE. Reasonable possibility means that there is evidence to suggest a causal relationship between the drug and the AE. An SAR implies a lesser degree of certainty about causality than AE, which means any AE caused by a drug.

CONFIDENTIAL

STUDY DRUG: NIVOLUMAB
SARAH CANNON DEVELOPMENT INNOVATIONS STUDY NUMBER:
FINAL PROTOCOL DATE: 07 FEB 2020

BMT 24
VERSION 7

11.1.5 Recording and Reporting of Adverse Events

Recording of Adverse Events

All AEs from any patient that occur during the course of the research study will be recorded in the eCRF, and the Investigator will give his or her opinion as to the relationship of the AE to the study drug treatment (i.e., whether the event is related or unrelated to study drug administration).

All AEs should be documented. A description of the event, including its date of onset and resolution, whether it constitutes a SAE or not, any action taken (e.g., changes to study treatment), and outcome, should be provided, along with the Investigator's assessment of causality (i.e., the relationship to the study treatment[s]). For an AE to be a suspected treatment-related event there should be at least a reasonable possibility of a causal relationship between the protocol treatment and the AE. Adverse events will be graded according to the NCI CTCAE v4.03, and changes will be documented.

If the AE is serious, it should be reported immediately to the Sarah Cannon Development Innovations Safety Department. Other untoward events occurring in the framework of a clinical study are to be recorded as AEs (i.e., AEs that occur prior to assignment of study treatment that are related to a protocol-mandated intervention, including invasive procedures such as biopsies, medication washout, or no treatment run-in).

Any clinically significant signs and symptoms; abnormal test findings; changes in physical examination; hypersensitivity; and other measurements that occur will be reported as an AE, and collected on the relevant eCRF screen.

Test findings will be reported as an AE if: the test result requires an adjustment in the study drug(s) or discontinuation of treatment, and/ or test findings require additional testing or surgical intervention, a test result or finding is associated with accompanying symptoms, or a test result is considered to be an AE by the Investigator.

Reporting Period for Adverse Events

All AEs, regardless of seriousness or relationship to nivolumab treatment (called study treatment), spanning from the start of study treatment until 100 calendar days after discontinuation or completion of study treatment as defined by the clinical study for that patient, are to be recorded on the corresponding screen(s) included in the eCRF.

All AEs resulting in discontinuation from the study should be followed until resolution or stabilization. All new AEs occurring during this period must be reported and followed until resolution unless, in the opinion of the Investigator, the AE or laboratory abnormality/ies are not likely to improve because of the underlying disease. In this case, the Investigators must record his or her reasoning for this decision in the patient's medical record.

After 100 days following the completion of protocol-specific treatment or discontinuation, only AEs, SAEs, or deaths assessed by the Investigator as treatment-related are to be reported.

CONFIDENTIAL

STUDY DRUG: NIVOLUMAB

SARAH CANNON DEVELOPMENT INNOVATIONS STUDY NUMBER:

FINAL PROTOCOL DATE: 07 FEB 2020

BMT 24

VERSION 7

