 - Left ventricular ejection fraction (LVEF) <45% as determined by multiple gated acquisition (MUGA) scan or echocardiogram (ECHO)
 - Corrected QT (QTc) interval >480 ms on screening electrocardiogram (ECG)
 - Unstable angina pectoris
 - Congestive heart failure (New York Heart Association (NYHA) \geq Grade 2 [Appendix B])
 - Acute myocardial infarction
 - Conduction abnormality not controlled with pacemaker or medication
 - Significant ventricular or supraventricular arrhythmias (patients with chronic rate-controlled atrial fibrillation in the absence of other cardiac abnormalities are eligible)
 - Valvular disease with significant compromise in cardiac function
14. Inadequately controlled hypertension (i.e., systolic blood pressure [SBP] >180 mmHg or diastolic blood pressure [DBP] >100 mmHg) (patients with values above these levels must have their blood pressure [BP] controlled with medication prior to starting treatment).
15. Serious active infection at the time of treatment, or another serious underlying medical condition that would impair the ability of the patient to receive protocol treatment.
16. Known diagnosis of human immunodeficiency virus, hepatitis B, or hepatitis C. Testing at baseline is not required.
17. Presence of other active cancers, or history of treatment for invasive cancer \leq 5 years. Patients with Stage I cancer who have received definitive local treatment and are considered unlikely to recur are eligible. All patients with previously treated in situ carcinoma (i.e., non-invasive) are eligible, as are patients with history of non-melanoma skin cancer.
18. Psychological, familial, sociological, or geographical conditions that do not permit compliance with the protocol.

CONFIDENTIAL

STUDY DRUG: NIVOLUMAB

SARAH CANNON DEVELOPMENT INNOVATIONS STUDY NUMBER:

FINAL PROTOCOL DATE: 07 FEB 2020

BMT 24

VERSION 7

3.3 **Discontinuation from Study Treatment**

Patients will be discontinued from study treatment for any of the following reasons:

- Disease progression
- Irreversible or intolerable toxicity or abnormal laboratory values thought to be related to drug toxicity
- Conditions requiring therapeutic intervention not permitted by the protocol
- Intercurrent illness (this will be at the Investigator's discretion)
- Inability of the patient to comply with study requirements
- Patient requests to discontinue treatment
- Patient withdraws consent from the study
- Non-compliance/lost to follow-up
- Pregnancy

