After discontinuation from protocol treatment, patients must be followed for AEs for 100 days after their last dose of nivolumab. All new AEs occurring during this period must be reported and followed until resolution, unless, in the opinion of the Investigator, these values are not likely to improve, because of the underlying disease. In this case, the Investigator must record his or her reasoning for this decision in the patients' medical records.

All patients who have Grade 3 or 4 laboratory abnormalities (per National Cancer Institute Common Terminology Criteria for Adverse Events [NCI CTCAE] v4.03) at the time of discontinuation must be followed until the laboratory values have returned to Grade 1 or 2, unless it is, in the opinion of the Investigator, not likely that these values are to improve. In this case, the Investigator must record his or her reasoning for making this decision in the patients' medical records.

4. **PATIENT REGISTRATION**

The patient must willingly consent after being informed of the procedures to be followed, experimental nature of the treatment, potential benefits, treatment alternatives, side effects, risks, and discomforts. Institutional Review Board (IRB) approval of this protocol and consent form is required. Eligible patients who wish to participate in the study will be enrolled into the study.

Registration must occur prior to the initiation of protocol therapy. Patients eligible to participate in the study may be enrolled through the Sarah Cannon Development Innovations Central Enrollment Desk. The enrollment desk may be reached by calling [contact]. Registration may be done: 1) via [contact] Monday through Friday, 8:30 a.m. to 4:30 p.m., Central Standard Time, or 2) via email at [contact]. Patient registration will be confirmed via email within 24 hours or by the next business day.

CONFIDENTIAL

STUDY DRUG: NIVOLUMAB

SARAH CANNON DEVELOPMENT INNOVATIONS STUDY NUMBER:

FINAL PROTOCOL DATE: 07 FEB 2020

BMT 24

VERSION 7

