7.4 End of Study Treatment

After withdrawal from or completion of protocol treatment, patients must be followed for AEs for 100 calendar days after the last dose of study drug. The following assessments will be performed:

- Physical examination, including measurement of weight and vital signs
- ECOG performance status
- AE assessment
- Concomitant medication review
- CBC, including 3-part differential and platelets
- CMP
- Serum or urine pregnancy test
- Research blood sample for correlative analysis

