7.6 Follow-up

Patients will be followed every month (± 1 week) for 3 months and then every 3 months thereafter from the date of last dose of nivolumab for up to 2 years. A research blood sample will be taken 1 year after the first dose of nivolumab. A phone call may be used to assess survival and to record initiation of an alternative form of treatment for lymphoma after response assessment at 1 year post-ASCT.

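### Treatment-emergent AEs have no end point, so the all-cause, serious and maximum-grade tables can take in toxicity of a new lymphoma therapy started within 100 days of the last dose

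*Combined protocol and SAP*

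**What the plan says.** Safety and tolerability of nivolumab is the primary objective (Section 2.1). Three sections set the collection window, and none makes an exception for a patient who has moved to another treatment:

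- Section 11.1.5: "All AEs, regardless of seriousness or relationship to nivolumab treatment (called study treatment), spanning from the start of study treatment until 100 calendar days", counted from when nivolumab is discontinued or completed. Beyond that, only events judged treatment-related are reported.
- Section 3.3: "After discontinuation from protocol treatment, patients must be followed for AEs for 100 days after their last dose of nivolumab". The reasons for stopping listed just before this include disease progression and "Conditions requiring therapeutic intervention not permitted by the protocol".
- Section 7.4: "After withdrawal from or completion of protocol treatment, patients must be followed for AEs for 100 calendar days after the last dose of study drug".

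Section 10.4.3 sets an analysis rule that has a start only: "Treatment-emergent AEs are those with an onset on or after the initiation of therapy". These events are "summarized using system organ class and preferred term for all patients in the Safety Population". Further summaries cover serious AEs, AEs by maximum grade, AEs leading to treatment discontinuation and related AEs.

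Two other places bear on new therapy. Section 5.3.2 says that a patient who needs another anticancer agent has to be withdrawn from the study before receiving it. Section 7.6 allows a phone call to "record initiation of an alternative form of treatment for lymphoma", but ties that call to the period after the 1-year post-transplant assessment. Section 10 uses the start of new therapy nowhere.

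**The concern.** A patient who progresses stops nivolumab and may be given another anti-lymphoma therapy while the 100-day window is still open. Read as written, the collection sections keep every event in that period whatever its cause, and Section 10.4.3 counts each of them as treatment-emergent. Toxicity of the next therapy would then appear in the all-cause, serious and maximum-grade summaries as part of nivolumab's safety profile.

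The distortion has a direction. It can only raise these all-cause rates, and it grows with the number of patients who relapse. With 35 treated patients, each additional patient moves a rate by almost 3 points. The study has no concurrent arm on which the safety tables could be calibrated, because the five control patients serve the immune-recovery comparison only.

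**Working it through.** **Inputs.** 35 treated patients (Section 5). From Section 10.2: 12-month PFS of 70% under the alternative and 50% under the null, Weibull shape 1 (exponential), 18 months' enrolment and 12 months' further follow-up. Up to 6 months of treatment (Section 5.2). A 100-day window, which is 100/30.4375 = 3.29 months. PFS runs from the first dose (Section 10.4.2).

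**Reproducing the plan's figure.** The hazard is λ = −ln(0.70)/12 = 0.02972 per month. The event probability is 1 − (e^(−12λ) − e^(−30λ))/(18λ) = 1 − (0.7000 − 0.4100)/0.5350 = 0.458, which agrees with the stated 0.4579. The same model with n = 36 and a two-sided 0.05 level gives 80.3% power, as stated. The hazard used below is therefore the plan's own.

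**Patients with a PFS event while AEs are being collected.**

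| 12-month PFS | Within 6 months of treatment | By 6 months + 100 days (9.29 months) |
|---|---|---|
| 70% | 1 − e^(−6λ) = 0.163; × 35 = 5.7 | 1 − e^(−9.29λ) = 0.241; × 35 = 8.4 |
| 50% | 0.293; × 35 = 10.3 | 0.415; × 35 = 14.5 |

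**How many could start new therapy inside the window.** The documents give no time from progression to next therapy. I assume a lag of 0 to 60 days and that every PFS event leads to new therapy. The count is 35 × (1 − e^(−λ(9.29 − lag))), with lag in months.

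- 70% PFS: 8.4 patients with no lag, 6.8 with a 60-day lag.
- 50% PFS: 14.5 and 12.1.

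These are upper-range counts. PFS events include deaths, and not every patient who progresses is treated again inside the window.

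**Effect on a Grade 3 or higher rate.** A maximum-grade table counts each patient once, so only patients whose first Grade 3 or higher event comes from the new therapy change it. The documents do not give that number.

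- 1 patient: 1/35 = 2.9 points.
- 3 patients: 3/35 = 8.6 points.
- All 5.7 with an event during treatment: 5.7/35 = 16 points. This requires that every one of them switches, has such an event from the new therapy and had none before.
- One illustrative set of assumptions: half switch, half of those have a Grade 3 or higher event, and 70% had none earlier. Then 5.7 × 0.5 × 0.5 × 0.7 = 1.0 patient, about 3 points.

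For scale, the 95% half-width of a proportion at n = 35 is at most 1.96 × √(0.25/35) = 0.166, about 17 points (normal approximation).

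**Scan timing.** Section 9 assesses progression at 6 months and 1 year after transplant, so detection is not smooth. Taking 6 months as 182 days, a patient who starts on day 45 leaves the window on day 45 + 182 + 100 = 327, before the 1-year scan. One who starts on day 180 stops on day 362 and stays in the window until day 462, so the 1-year scan falls inside it. The exponential counts therefore indicate order of magnitude only.

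**The case against.** The strongest objection is Section 5.3.2. If a patient must leave the study before another anticancer agent is given, and Section 11.1.5 opens by limiting recording to events during the study, collection may end before the new therapy starts and nothing enters the tables. This stands as an ambiguity, not as a rebuttal. Sections 3.3, 7.4 and 11.1.5 tie the 100 days to stopping treatment, and no section says that withdrawal under 5.3.2 ends it. Sites could follow different rules. Equally, a reader might infer that next-line toxicity certainly enters the tables, and the documents do not establish that either.

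A reader might also infer that the tables measure relapse itself. They largely do not. Section 11.3.1 keeps documented progression out of SAE reporting, Section 11.3.4 sends deaths due solely to progression to a separate form, and Section 11.3.7 treats metastasis and its symptoms as progression. Only toxicity of the subsequent treatment is at issue.

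Two planned tables are largely protected. Therapy given after nivolumab has stopped cannot cause an AE leading to its discontinuation. Relatedness is judged under Section 11.1.6, which weighs concomitant therapies, although that is an open-label judgement in a single treated arm. It does not help the all-cause, serious and maximum-grade tables.

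All-cause collection to 100 days is a cautious choice for a drug whose immune effects may appear late, and I do not dispute it. Nor does any hypothesis test, interim analysis or stopping threshold depend on these rates. That limits the consequence to description and interpretation, but safety is the primary objective and description is all it will receive.

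Finally, it is tempting to say that next therapy usually starts within 100 days, or that its date is already on file. No section supports the first. On the second, Section 7.6 does not expressly require a start date inside the window, and Appendix E schedules no concomitant-medication review in follow-up.

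**Conclusion.** The point holds as a gap in the TEAE definition. Nothing in Section 10.4.3 ends or splits the count at new anti-lymphoma therapy, so the all-cause, serious and maximum-grade summaries can include its toxicity. Whether they will depends on how Section 5.3.2 is reconciled with Sections 3.3, 7.4 and 11.1.5.

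The plausible size is about 3 to 9 points on a Grade 3 or higher rate. That rests on an assumed 1 to 3 patients whose first such event comes from the new therapy, out of about 6 with a PFS event during treatment and about 8 by the end of the window at 70% 12-month PFS. A reader might take 16 points as the expected shift. It is an extreme upper bound that needs all 5.7 patients to be affected. The plausible shift is smaller than the sampling uncertainty at n = 35, but unlike sampling error it always runs in one direction. The counts assume a constant hazard from the first dose, PFS events that are progressions followed by new therapy, and full 6-month treatment unless progression occurs. No sample-size figure changes.

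**What to change.** Leave the 100-day collection as it is and change the tabulation:

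1. In Section 10.4.3, give TEAEs an end. Present all-cause TEAEs, SAEs and AEs by maximum grade up to the earlier of 100 days after the last dose and the day before the first new anti-lymphoma therapy.
2. Tabulate events that fall after that point but within the 100 days separately.
3. Keep every event judged related to nivolumab in the main tables, whenever it occurs.
4. Reconcile Section 5.3.2 with Sections 3.3, 7.4 and 11.1.5, so that all sites know whether AE collection continues after a patient is withdrawn to receive another agent.
5. Confirm that the eCRF captures the start date of new therapy within the window, and add the field if it does not.

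The cost is one analysis rule, one clarification and possibly one date field. No data are discarded. The downside is that a late immune event judged unrelated, with onset after new therapy, appears in the separate table and not in the main one. Showing the two tables together keeps it visible.
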